6.6.2. Laboratory Data

Laboratory parameters will be summarized descriptively over time, and as described in Section 3.5.2. Individual plots of absolute values in Platelet Count, aPTT, INR vs time for participants with Platelet Count<100,000/mm3 after Day 1 to Week 48 will be produced as well as individual plots of absolute values in TG, FPG, FPI, ApoC3 vs time for participants with Fasting TG ≥ 400 mg/dL after Day 1 to Week 48.

6.6.3. Vital Signs

Changes from baseline in systolic blood pressure, diastolic blood pressure and pulse rate will be summarized by treatment and time. The number (%) of participants with maximum increases from baseline will be tabulated by treatment as defined in Section 3.5.3. Numbers and percentages of participants meeting the categorical criteria will be provided and individual values listed in the study report. No formal inferential statistics will be applied to the vital signs data.

6.6.4. Electrocardiograms

Changes from baseline for the ECG parameters QT interval, heart rate, QTcF interval, PR interval, and QRS interval will be summarized by treatment and time. For purposes of reporting study-level results, QTcF interval will be derived using Fridericia's heart rate correction formula applied to databased QT interval, and RR interval. The number (%) of participants with maximum increases from baseline will be tabulated by treatment as defined in Section 3.5.3. Numbers and percentages of participants meeting the categorical criteria will be provided and individual values listed in the study report. No formal inferential statistics will be applied to the ECG data.

7. INTERIM ANALYSES

7.1. Introduction

Interim analyses (IAs) will be performed to assess safety after approximately 33%, 67%, and 100% of the planned total sample size has been randomized in the study (and these would primarily be for External Data Monitoring Committee (E-DMC) safety reviews while the study is ongoing). If required, interim analysis results from a single IA may be used for

other purposes such as: internal business decisions regarding future study planning, conducting a sample size re-estimation, adapting the safety-related endpoints in the study after the interim analysis, or early unblinding to facilitate Population PK/PD model development. Before any interim analysis is instigated, the details of the objectives, decision criteria, dissemination plan, and method of maintaining the study blind as per Pfizer's SOPs will be documented and approved in an E-DMC charter or a separate interim analysis plan as needed.

7.2. Interim Analyses and Summaries

Any analyses and summaries to be included in the E-DMC reviews will be documented in the E-DMC Charter or a separate interim analysis plan.

9. APPENDICES

Appendix 1. Summary of Efficacy Analyses

Endpoint	Analysis Type	Population	Data Inclusion and Rules for Handling Intercurrent Events and Missing Data	Analysis Model
Primary: Proportion of participants achieving	Summary	Evaluable	Observed data.	N/A
participants achieving centrally adjudicated resolution of NASH without worsening of fibrosis or improvement in fibrosis by ≥1 stage without worsening of NASH, or both, at Week 48	Main analysis (Estimand 1.1)	Evaluable	Participants who discontinue treatment or from the study due to lack of efficacy or toleration prior to Week 48 or if they do not have evaluable Week 48 Biopsy data, will be considered to be non-responders. All data collected at or after withdrawal from treatment for other reasons (not related to lack of efficacy or toleration) will be included.	Bayesian Emax for DR, Logistic Regression for pairwise comparisons
	Sensitivity Analyses	Evaluable	Same as main analysis, but may utilize alternative prior distributions for Bayesian Emax modelling.	Bayesian Emax for DR
	Supplementary analysis (Estimand 1.2)	Evaluable	All data collected before or at the time of treatment withdrawal will be included. Endpoint data collected after treatment withdrawal will be censored. Analysis will be	Bayesian Emax for DR, Logistic Regression for pairwise comparisons

Endpoint	Analysis Type	Population	Data Inclusion and Rules for Handling Intercurrent Events and Missing Data	Analysis Model
			carried out under the assumption that missing biopsies at Week 48 are missing at random conditional on dose and the strata formed by the covariates (fibrosis status and T2DM status).	
Secondary: Proportion of participants achieving	Summary	Evaluable	Observed data.	N/A
centrally adjudicated resolution of NASH without worsening of fibrosis at Week 48	Main analysis (Estimand 2.1)	Evaluable	Participants who discontinue treatment or from the study due to lack of efficacy or toleration prior to Week 48 or if they do not have evaluable Week 48 Biopsy data, will be considered to be non-responders. All data collected at or after withdrawal from treatment for other reasons (not related to lack of efficacy or toleration) will be included.	Bayesian Emax for DR, Logistic Regression for pairwise comparisons
	Sensitivity Analyses	Evaluable	Same as main analysis, but may utilize alternative prior distributions for Bayesian Emax modelling.	Bayesian Emax for DR

Endpoint	Analysis Type	Population	Data Inclusion and Rules for Handling Intercurrent Events and Missing Data	Analysis Model
Secondary: Proportion of participants achieving	Summary	Evaluable	Observed data.	N/A
centrally adjudicated improvement in fibrosis by ≥1 stage without worsening of NASH at Week 48	Main analysis (Estimand 2.2)	Evaluable	Participants who discontinue treatment or from the study due to lack of efficacy or toleration prior to Week 48 or if they do not have evaluable Week 48 Biopsy data, will be considered to be non-responders. All data collected at or after withdrawal from treatment for other reasons (not related to lack of efficacy or toleration) will be included.	Bayesian Emax for DR, Logistic Regression for pairwise comparisons
	Sensitivity Analyses	Evaluable	Same as main analysis, but may utilize alternative prior distributions for Bayesian Emax modelling.	Bayesian Emax for DR
Secondary: Proportion of participants achieving	Summary	Evaluable	Observed data.	N/A
centrally adjudicated improvement in fibrosis by ≥2 stages without worsening of NASH at Week 48	Main analysis (Estimand 2.3)	Evaluable	Participants who discontinue treatment or from the study due to lack of efficacy or toleration prior to Week 48 or if they do not have evaluable Week 48 Biopsy data, will be considered to be non-	Bayesian Emax for DR, Logistic Regression for pairwise comparisons

Endpoint	Analysis Type	Population	Data Inclusion and Rules for Handling Intercurrent Events and Missing Data	Analysis Model
			responders. All data collected at or after withdrawal from treatment for other reasons (not related to lack of efficacy or toleration) will be included.	
	Sensitivity Analyses	Evaluable	Same as main analysis, but utilize alternative prior distributions for Bayesian Emax modelling.	Bayesian Emax for DR
Secondary: Proportion of participants achieving	Summary	Evaluable	Observed data.	N/A
centrally adjudicated improvement of ≥2 points in Total NAFLD Activity Score (NAS) without worsening of fibrosis at Week 48	Main analysis (Estimand 2.4)	Evaluable	Participants who discontinue treatment or from the study due to lack of efficacy or toleration prior to Week 48 or if they do not have evaluable Week 48 Biopsy data, will be considered to be non-responders. All data collected at or after withdrawal from treatment for other reasons (not related to lack of efficacy or toleration) will be included.	Bayesian Emax for DR, Logistic Regression for pairwise comparisons

Endpoint	Analysis Type	Population	Data Inclusion and Rules for Handling Intercurrent Events and Missing Data	Analysis Model
	Sensitivity Analyses	Evaluable	Same as main analysis, but utilize alternative prior distributions for Bayesian Emax modelling.	Bayesian Emax for DR
Secondary: Percentage change in liver fat	Summary	Evaluable	Observed data.	N/A
(assessed via MRI- PDFF) at Week 48	Main analysis (Estimand 2.5)	Evaluable	All data collected before or at the time of withdrawal will be included. Endpoint data collected after treatment withdrawal will be censored. Missing data at Week 48 will not be imputed. MMRM will be used to obtain LS mean estimate at Week 48 for each dose, which will then be used in fitting the Bayesian Emax model.	Bayesian Emax for DR, ANCOVA for pairwise comparisons
	Sensitivity Analyses	Evaluable	Same as main analysis, but utilize alternative prior distributions for Bayesian Emax modelling.	Bayesian Emax for DR
	Summary	Evaluable	Observed data.	N/A

Endpoint	Analysis Type	Population	Data Inclusion and Rules for Handling Intercurrent Events and Missing Data	Analysis Model
Exploratory: Proportion of participants achieving improvement in fibrosis by ≥1 stage independent of changes in NAS, at Week 48	Main analysis (Estmand 3.2)	Evaluable	Participants who discontinue treatment or from the study due to lack of efficacy or toleration prior to Week 48 or if they do not have evaluable Week 48 Biopsy data, will be considered to be non-responders. All data collected at or after withdrawal from treatment for other reasons (not related to lack of efficacy or toleration) will be included.	Bayesian Emax for DR, Logistic Regression for pairwise comparisons
Exploratory: Proportion of participants achieving	Summary	Evaluable	Observed data.	N/A
resolution of NASH without worsening of fibrosis and improvement in fibrosis by ≥1 stage without worsening of NASH, at Week 48	Main analysis (Estmand 3.3)	Evaluable	Participants who discontinue treatment or from the study due to lack of efficacy or toleration prior to Week 48 or if they do not have evaluable Week 48 Biopsy data, will be considered to be non-responders. All data collected at or after withdrawal from treatment for other reasons (not related to lack of efficacy or toleration) will be included.	Bayesian Emax for DR, Logistic Regression for pairwise comparisons

Endpoint	Analysis Type	Population	Data Inclusion and Rules for Handling Intercurrent Events and Missing Data	Analysis Model
Exploratory: Proportion of participants with	Summary	Evaluable	Observed data.	N/A
Worsening of ≥2 points in Total NAS (defined as an increase of at least 2 points in Total NAS compared to baseline) independent of changes in fibrosis at Week 48	Main analysis (Estimand 3.1)	Evaluable	Participants who discontinue treatment or from the study due to lack of efficacy or toleration prior to Week 48 or if they do not have evaluable Week 48 Biopsy data, will be considered to be responders (i.e. they will be assumed to have worsened). All data collected at or after withdrawal from treatment for other reasons (not related to lack of efficacy or toleration) will be included.	Bayesian Emax for DR, Logistic Regression for pairwise comparisons
Exploratory: Proportion of participants with	Summary	Evaluable	Observed data.	N/A
progression of fibrosis by ≥1 stage (defined as an increase of at least 1 stage in the Brunt- Kleiner scale compared to baseline) independent of changes in NAS at Week 48	Main analysis (Estmand 3.1)	Evaluable	Participants who discontinue treatment or from the study due to lack of efficacy or toleration prior to Week 48 or if they do not have evaluable Week 48 Biopsy data, will be considered to be responders (i.e. they will be assumed to have worsened). All data collected at or after	Bayesian Emax for DR, Logistic Regression for pairwise comparisons

Endpoint	Analysis Type	Population	Data Inclusion and Rules for Handling Intercurrent Events and Missing Data	Analysis Model
			withdrawal from treatment for other reasons (not related to lack of efficacy or toleration) will be included.	
Exploratory: Proportion of participants with	Summary	Evaluable	Observed data.	N/A
progression of fibrosis by ≥1 stage and worsening of ≥2 points in Total NAS at Week 48	Main analysis (Estimand 3.1)	Evaluable	Participants who discontinue treatment or from the study due to lack of efficacy or toleration prior to Week 48 or if they do not have evaluable Week 48 Biopsy data, will be considered to be responders (i.e. they will be assumed to have worsened). All data collected at or after withdrawal from treatment for other reasons (not related to lack of efficacy or toleration) will be included.	Bayesian Emax for DR, Logistic Regression for pairwise comparisons

Appendix 2. Data Derivation Details

Appendix 2.1. Definition and Use of Visit Windows in Reporting

Each collected assessment will be mapped to its actual visit window according the following algorithm described in the table below:

Visit label	Protocol defined Window (days)	Visit	Visit window as part of final reporting*
			For efficacy, PD, PK and safety endpoints
Pre-Qualification	N/A	1	N/A
Screen 1	N/A	2	N/A
Screen 2	N/A	3	N/A
Run-In	N/A	3	N/A
Week -2	-14 ± 4	4	Between Week 0 and Week -2, data are used to define baseline
Week 0	1	5	Baseline will be result closest prior to dosing on randomized regimen on Day 1 [Visit 5] Window for baseline measurements is from Day -22 to Day 1 [Visit 5] pre-dose (The only exception is for Height, for which any measurement from PreQ to Day 1 pre-dose can be used, and for Fibroscan® for which the last evaluable measurement from SCR1 to Day 1 pre-dose can be used) Label as 'BASELINE'
Week 2	14 ± 4	6	
			'Date of assessment' – 'Baseline date' + 1 = [8, 21]; ie, - 6 days to +7 days
Week 4	28 ± 4	7	'Date of assessment' – 'Baseline date' + 1 = [22, 35]; ie, -6 days to +7 days
Week 6	42 ± 4	8	'Date of assessment' – 'Baseline date' + 1 = [36, 49]; ie, -6 days to +7 days
Week 8	56 ± 4	9	'Date of assessment' – 'Baseline date' + 1 = [50, 70]; ie, -6 days to +14 days
Week 12	84 ± 4	10	'Date of assessment' – 'Baseline date' + 1 = [71, 98]; ie, -13 days to +14 days
Week 16	112 ± 4	11	'Date of assessment' – 'Baseline date' + 1 = [99, 140]; ie, -13 days to +28 days
Week 24	168 ± 4	13	'Date of assessment' – 'Baseline date' + 1 = [141, 196]; ie, -27 days to +28 days
Week 32	224 ± 4	15	'Date of assessment' – 'Baseline date' + 1 = [197, 252]; ie, -27 days to +28 days
Week 36**	252 ± 4	16	'Date of assessment' – 'Baseline date' + 1 = [197, 308]; ie, -55 days to +56 days
Week 40	280 ± 4	17	'Date of assessment' – 'Baseline date' + 1 = [253, 308]; ie, -27 days to +28 days
Week 48	336 ± 4	19	'Date of assessment' – 'Baseline date' + 1 = [309, 343]; ie, -27 days to +7 days
Week 50 (1st		20	'Date of assessment' – 'Date of last dose' + 1 = [7, 27];
Follow-up visit)			ie, any time after 7 days and up to 28 days after last dose.
Week 52 (2nd	≥28- and ≤35- days		'Date of assessment' – 'Date of last dose + 1 ≥ 28;
Follow-up visit)	post last dose at	1	ie, any time after 28 days after last dose

Visit label	Protocol defined Window (days)	Visit	Visit window as part of final reporting*
			For efficacy, PD, PK and safety endpoints
	Week 48 visit in the protocol		

Note: * permitted to be wider than window defined in protocol for purposes of reporting data by nominal visit

Special considerations:

- For participants withdrawn early, the 1st follow-up visit window (F/U) will include data
 up to 4 days after the last dose of study medication, and the visit label is defined in
 accordance with the nominal label as recorded on the "E_TERM/FOLLOW_UP"
 Administration CRF.
- Data from planned and unplanned visits will be windowed, as well as data on study drug and for participants who may have discontinued study medication but are continuing in the study.
- If 2 or more observations fall within the visit window for Week N (regardless of whether
 they are planned or unplanned), the observation used will be the one closest to Day 7N
 (randomization day is Day 1). If the 2 closest observations are equidistant from Day 7N,
 the earlier observation will be used.
- An assessment is considered 'on treatment' if the following is true:
 - 'Date (time when databased) of assessment' > 'Baseline date (time)' and ≤'Last dose date (time)'
- For Liver Biopsy, MRI and Fibroscan® assessments, any Week 48 assessments would be considered to be evaluable, regardless of when they were performed relative to the last dose.
- In addition, the Fibroscan® endpoint of CAPTM and VCTETM will require conduct of FibroScan® following a fast of at least 4 hours and based on ≥ 10 valid measurements, to be evaluable for analysis, and an additional criterion should be applied for liver stiffness (VCTETM) only:
 - For median stiffness (kPa) ≥7.1 kPa:
 - Interquartile stiffness Range (kPa) divided by median stiffness (kPa) x 100 should be ≤30%
 - This needs to be derived from the Interquartile stiffness Range (kPa) and Median stiffness (kPa) as recorded in the database
 - For median stiffness (kPa) <7.1 kPa
 - any Interquartile stiffness Range (kPa) result is acceptable, so this additional criterion does not need to be applied to these values

^{**} This visit window will only be used for Patient Reported Outcomes reported at Week 36. The other postbaseline visits at which these data are collected are Weeks 12, 24 and 48, therefore the Week 32 and Week 40 analysis windows have not been adjusted to allow for the Week 36 analysis window.

- Assesment of evaluable CAPTM (dB/m) result will not use Interquartile attentuation Range (dB/m).
- For Fibroscan® Baseline derivation, the last evaluable measurement from SCR1 to Day 1 pre-dose can be used (i.e. closest results obtained prior to dosing on Day 1 (Visit 5)).
- Patient Reported Outcomes: All PRO endpoints will be analyzed according to the analysis windows above (and the Week 36 analysis window will only be used for the PROs completed at Week 36). Note that only the daily assessments recorded in the e-Diary prior to dosing on Day 1 [Visit 5] will be included in the derivation of Baseline NASH Symptom Diary scores. Any daily assessments captured in the e-Diary on Day 1 or later will be excluded from the Baseline scores. For PGI-S, as this is recorded twice at each visit, the records will be selected based on the below method:

Closest to Target (first) – Selects the record closest to the target. If two records are equi-distant from the target (before and after), select the 1st record.

- For the following assessments, the above visit windows will not be used:
 - Liver Biopsy:

For liver biopsy assessments, any pre-randomization biopsy data will be considered to be 'Baseline', and any post-randomization biopsy data collected on or after the Week 24 visit will be considered to be 'Week 48/End of Study'. This is so that any liver biopsies performed at the 'early termination' visit, which will be an unplanned visit (after Week 24), can be windowed appropriately so that data will be summarized and included in the analysis as required.

 MRI: All MRI endpoints will be analyzed according to the nominal visit to which they relate.

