Weeksa Relative to Dosing on Day 1				-6	-2	0	2	4	6	8	12	16	20	24	28	32	36	40	44	48	50	52b)/C
Visit #	0	1	2	3	4	5	6	7	8	9	10	11	12	13	14	15	16	17	18	19	20	21	IP I

- a. Defined relative to Day 1 with permitted ± 4-day window for each visit starting at Visit 4/Baseline; for example: Week -2 = 14 (±4) days before Day 1; Week 4 = 28 (±4) days post Day 1
- b. Run-In Visit required to be on site if changes to background medications are being made otherwise, Run-In Visit permitted as a telephone contact on the same day or up to 4 days post conduct of SCR2 liver biopsy; post randomization, telephone contact visits can be switched to on-site visits for follow up of TEAEs and/or abnormal laboratory tests; Week 52 visit at ≥28- and ≤35- days post last dose of study intervention
- Procedures to be performed as soon as practically possible after decision to stop study intervention but stay in study with continuation of scheduled visits or permanently withdraw from study
- d. Test results to be reviewed by medically qualified site staff and deemed acceptable before progression to next visit; for example: PreQ results must be reviewed prior to conduct of SCR1
- e. Collections to occur only if visit is an on-site visit; collections to be skipped if visit is via telephone contact
- f. In addition to blood collection, date and time of blood draw and date/time of previous two doses prior to each blood draw related to PK to be captured as part of sites' source documents
- g. Collection to occur between 0.5-1.5 hours post dose (at Week 2 and Week 8 visits), between 1.5-2.5 hours post dose (at Week 12 visit), and between 3-8 hours post dose (at Week 16 visit)
- At each of these visits, test results to be reviewed by a medically qualified site staff and deemed acceptable to continue participation in study

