8.1.3. Patient-Reported Outcomes

this work, if undertaken.

All PRO assessments are implemented using sponsor-provided ePRO device and completed by the participants at home, or at an on-site visit, as per the SoA-Table A1 and Table 4.

Table 4. Patient-Reported Outcome Measures Planned in Study C2541013

Measure	Frequency – refer to SoA-Table A1	Number of questions	Estimated Completion time	Assessment
NASH-Check	 Visit 4/Baseline 	31	8 minutes	On-site
	- Week 24/Visit 13			
	 Week 48/ Visit 19 			
NASH Symptom	Once-a-day for a 14 consecutive day period -	5	2 minutes	At home,
Diary (abdominal	 During the interval between Visit 4/ 			except when
pain, bloating,	Baseline and 1-day prior to Day 1/Visit 5			noted as
fatigue, sleep, and	- Starting at -			On-site
daytime	 Week 12/Visit 10^a 			
sleepiness)	 Week 24/Visit 13^a 			
	 Week 36/Visit 16^a (T) 			
	 Prior to Week 48/Visit 19^b 			
NASH PGI-S	Twice during a 14-day period -	2	3 minutes	
	 During the interval between Visit 4/ 			
	Baseline and 1-day prior to Day 1/Visit 5			
	– Starting at –			
	 Week 12/Visit 10^a 			
	 Week 24/Visit 13^a 			
	 Week 36/Visit 16^a (T) 			
	 Prior to Week 48/Visit 19^b 			
NASH PGI-C	Once during a 14-day period -	2		
	– Starting at –			
	 Week 12/Visit 10^a 			
	 Week 24/Visit 13^a 			
	 Week 36/Visit 16^a (T) 			
	Week 48/Visit 19 – On-site			
PROMIS Fatigue	 Visit 4/Baseline (completed On-site) 	9		
Custom 9-Item	Plus, once during a 14-day period -			
Version	- Starting at -			
("Past 7 days"	 Week 12/Visit 10^a 			
recall)	 Week 24/Visit 13^a 			
	 Week 36/Visit 16^a (T) 			
	Week 48/Visit 19 – On-site			

Table 4. Patient-Reported Outcome Measures Planned in Study C2541013

Measure	Frequency – refer to SoA-Table A1	Number of	Estimated	Assessment
		questions	Completion	
			time	

- a. Site staff required to activate the visit confirmation on site-specific sponsor-provided ePRO device, as part of these on-site/telephone visits in order to activate participants ability to start completing these data collections on participant-specific sponsor-provided device, at home

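### The Week 12 PRO window closes on Day 98, so PROMIS Fatigue or PGI-C records made late in a permitted 14-day collection period are labelled Week 16, where no PRO is scheduled

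*SAP*

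**What the plan says.** SAP Appendix 2.1 maps each assessment to a visit by its date. Week 12 is "Date of assessment' – 'Baseline date' + 1 = [71, 98]; ie, -13 days to +14 days" and the next window, Week 16, is "Date of assessment' – 'Baseline date' + 1 = [99, 140]; ie, -13 days to +28 days". Liver biopsy and MRI are exempt from these windows. PROs are not: "All PRO endpoints will be analyzed according to the analysis windows above". Week 36 alone has its own PRO row, with the footnote "This visit window will only be used for Patient Reported Outcomes reported at Week 36". The same footnote names Weeks 12, 24 and 48 as the other post-baseline PRO visits.

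Protocol Section 8.1.3, Table 4, starts four collections at Week 12/Visit 10:

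- the NASH Symptom Diary ("Once-a-day for a 14 consecutive day period");
- PGI-S, twice in 14 days;
- PGI-C, once in 14 days;
- PROMIS Fatigue, once in 14 days.

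Footnote a to Table 4 has site staff activate the visit on the device before the participant can begin, so the period cannot start before the visit. Neither Table 4 nor the Schedule of Activities has a PRO at Week 16. On visit timing, the Schedule of Activities says "Defined relative to Day 1 with permitted ± 4-day window for each visit starting at Visit 4/Baseline".

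**The concern.** A window centred on the visit suits an assessment made at the visit. The Week 12 PROs are made during the two weeks after it. The Week 12 window allows 14 days after its target and the collection period is 14 days long, so little or nothing is left for a late visit.

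The SAP dealt with this elsewhere. The Week 36 PRO-only window, [197, 308], is exactly the Week 32 window [197, 252] joined to the Week 40 window [253, 308]. Nothing equivalent was done at Week 12, although Week 16 is equally empty of PROs.

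What is at stake is the visit label of otherwise valid records. PROMIS Fatigue change from baseline is listed in SAP Section 6.3.6 for an MMRM with treatment-by-week terms and an unstructured covariance. A few records at a week nobody planned would add a poorly supported level to that model. Section 5.2.2 considers compound symmetry if the unstructured model does not converge. The SAP does not say whether such a level is kept or dropped.

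**Working it through.** **The plan's figure.** With the SAP target of Day 84, 84 − 13 = 71 and 84 + 14 = 98. This reproduces [71, 98].

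**Two day counts.** The protocol counts days after Day 1 ("Week 4 = 28 (±4) days post Day 1"), so Week 12 is 84 days after Day 1. The SAP counts the baseline date as Day 1, which makes that visit Day 84 + 1 = 85. The SAP's own target is Day 7N ("the observation used will be the one closest to Day 7N"), which is Day 84 for Week 12. Both are shown.

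**Formula.** If the first possible entry is on the visit day and the visit is v days late, the last day of the period is (85 or 84) + v + 13. Days after Day 98 fall in Week 16.

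| Visit 10 | From Day 85 | Days after Day 98 | From Day 84 | Days after Day 98 |
|---|---|---|---|---|
| On time | 85–98 | 0 | 84–97 | 0 |
| 1 day late | 86–99 | 1 | 85–98 | 0 |
| 2 days late | 87–100 | 2 | 86–99 | 1 |
| 3 days late | 88–101 | 3 | 87–100 | 2 |
| 4 days late | 89–102 | 4 | 88–101 | 3 |

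If entries begin the day after the visit, every range moves one day later. The latest permitted case is then Days 90–103, with 5 days in Week 16 and 14 − 5 = 9 in Week 12.

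**By instrument.**

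- *PROMIS Fatigue and PGI-C.* There is one record in the 14 days. If it is dated after Day 98, the participant has no Week 12 value and a Week 16 value instead.
- *PGI-S.* There are two records, and Appendix 2.1 takes the one closest to target. The Week 12 value is lost only if no record is dated by Day 98. A second record after Day 98 would carry a Week 16 label, but the Week 12 value stands.
- *NASH Symptom Diary.* The effect depends on whether entries are windowed singly or as one period (see the objection).
- *NASH-CHECK.* It is not collected at Week 12 and is unaffected.

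**Weeks 24 and 36.** With the visit 4 days late, the Week 24 period is Days 173–186, inside [141, 196], and the Week 36 period is Days 257–270, inside [197, 308]. Neither spills over.

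**Check of the remedy.** Joining Week 12 to Week 16 gives [71, 140]. The latest permitted period, Days 90–103, then lies wholly inside it. The earliest permitted Week 24 visit is 169 − 4 = Day 165, so no other scheduled PRO falls in Days 99–140.

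**The case against.** The strongest reply is that the damage is small and that several larger claims a reader might draw do not follow. Most of this stands.

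- **Diary scores.** A reader might infer that Week 12 diary averages are cut short or lost. SAP Appendix 2.3.3 averages the diary over the 14-day assessment period and refers to protocol Table 4 for that period. On that rule a late visit removes nothing. Appendix 2.1 can be read as windowing each entry by its date, and the SAP does not settle which applies. Even with day-by-day windowing, a permitted visit leaves at least 9 entries, above the minimum of 7, and the 5 or fewer stray days are too few for a Week 16 score.
- **Long delays.** Protocol Section 8.2 favours holding visits late after COVID-19 isolation, and a reader might infer missing diary scores from that. By the protocol count it takes a delay of 8 days to leave only 6 entries (Days 93–98). That is beyond the 4 days permitted, and it also presumes day-by-day windowing.
- **PGI-C in the MMRM.** PGI-C has no baseline collection in Table 4 and is listed only as an absolute score. The MMRM needs a baseline covariate, so PGI-C does not fit it. For PGI-C the effect is on the summary by visit.
- **A share of participants.** Completion is prompted by the device or site, and the prompt days are not given. If every once-only record is made on the first day, none moves. If prompts come late in the period, more do. Any percentage would only restate an assumption.

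None of this reaches the narrow point. For an instrument completed once, the date decides the label, and Appendix 2.1 labels Days 99 onward as Week 16.

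**Conclusion.** The point holds in its narrow form. Read as written, Appendix 2.1 gives the wrong visit label to a once-only Week 12 PROMIS Fatigue or PGI-C record dated after Day 98. With entries from the visit day and a visit within the permitted window, up to 4 of the 14 possible days are exposed by the protocol's count, or 3 from the SAP's target. If entries begin the day after the visit, the maximum by the protocol's count is 5.

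The number of records affected is unknown. It depends on the prompt days and on how late visits run, and the documents give neither. The diary question is an ambiguity between Appendices 2.1 and 2.3.3, not a demonstrated loss of data. All the endpoints concerned are tertiary or exploratory, and no primary, secondary or safety result is touched. It is a minor correction that is worth making because it costs almost nothing.

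**What to change.** In SAP Appendix 2.1:

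1. Add a PRO-only Week 12 row with window [71, 140], built like the PRO-only Week 36 row, and extend that row's footnote to cover it.
2. State that the Week 16 window is not used for PROs.
3. State that NASH Symptom Diary entries are assigned to a visit as one 14-day assessment period under Appendix 2.3.3, not day by day.

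Any upper limit of Day 103 or later would cover permitted visits. Day 140 is preferable because it follows the sponsor's own Week 36 construction and leaves no gap before the Week 24 window opens on Day 141.

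The cost is one table row, a footnote edit and two sentences in the SAP. It needs no new data and no protocol amendment.
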